OSLO UNIVERSITETSSYKEHUS -HF RIKSHOSPITALET

Research Protocol

[name] – PhD student Department of Nutrition, University of Oslo and Oslo Universityhispital

June 2018

1. Project title

Effect of FODMAP restriction on persistent GI-symptoms in coeliac patients

2. Introduction

The project targets a major disease group in Norway where there is an unmet and unresolved clinical need. The project is very patient-oriented and will contribute to clinical tools in management of coeliac disease. The research will immediately benefit the patient group.

Coeliac disease is a common condition, which affects at least 1-2 % of the population and the prevalence is increasing [2]. Many coeliacs worldwide are undiagnosed. This also applies in Norway, where Norwegian Coeliac Disease Association (NCF) has ca. 10 000 members, while it is expected that at least 50-100 000 people in the Norwegian population have the disease. There is no good disease registry on how many people have been diagnosed. Coeliac disease is characterised by small intestine is damage by an inflammatory process in the mucosa [2, 3]. This inflammation triggered by wheat gluten and similar proteins of rye and barley. Detection of tottering changes in tissue samples taken with gastroscopy, blood tests examining serum antibodies to the enzyme Transglutaminase 2 (TG2) or to Deamidated gliadin peptides (DGP) is necessary to detect the disease. It is important that these tests are taken while the patient eats gluten, because they will normalize on a gluten free diet. Follow-up of the patients is either done by serology or by serology and biopsy. Mucosal recovery is a treatment goal, persistent inflammation predisposes to malignant disease [4]. Serology is less sensitive than biopsy in this matter.

The symptoms of coeliac disease are only partially explained by the small bowel injury [2]. Micronutrient deficiency such as iron, folic acid and vitamin D as well as osteoporosis is common at the time of diagnosis. These deficiencies are not obligate nor typically for coeliac disease as they also exist in other diseases. Discomfort from stomach with flatulence, bloating, diarrhoea or constipation is very common in the disease but does not affect everyone. A feeling of constant tiredness and difficulty concentrating called "foggy brain" is also common. In addition to these characters is a plethora of associated diseases such as hypothyroidism, diabetes, infertility, arthritis and skin lesions. Patients with coeliac disease have increased mortality because of a certain cancer hazard. They are prone to lymphomas and adenocarcinomas, but the risk is reduced with treatment by gluten free diet [2].

2.1 Needs description

Treatment of coeliac disease

The treatment of coeliac disease is today a lifelong gluten free diet, although alternative treatment options are being developed [5]. A gluten free diet means a diet devoid of wheat, rye, barley and closely related cereals. This treatment provides in most cases good results. Monitoring and teaching by a clinical dietician are particularly important for coeliacs, and this practice group is invaluable. However, patients are dependent of gastroenterologists` and GP`s awareness of the disease, and there is a continuous effort to improve this knowledge.

Although treatment with gluten free diet usually gives good results, there are many patients who have continued ailments from their stomach or with their general health after they have started a diet [6-10]. This could be due to either failure to adapt to a really strict diet (compliance problems due to lack of knowledge or lack of motivation), or it could be symptoms compatible with, and caused by factors giving, what is referred to as "irritable bowel syndrome" (IBS). Data from US suggest this to affect 10-20 % of coeliac patients [8], whereas a recent Finnish study found that 23 % of long-term well-treated coeliac patients still had persistent gastrointestinal symptoms [10].

There have been no studies on persistent gastro-intestinal symptoms in celiac patients from Norway, but with our broad clinical experience from the patient group, we believe that the numbers are at least at this level in Norway. We specifically aim at investigating the impact of FODMAPon this frequent condition with

persistent symptoms in coeliac disease patients on a gluten free diet.

The FODMAP concept

The term is short for Fermentable Oligo-, Di-, Monosaccharides And Polyols (FODMAP); dietary carbohydrates and other substances that are relatively resistant to intestinal digestion and absorbtion and as a result they pass

on to the large bowel where they meet a rich bacterial flora able to ferment these substances. FODMAP rich food includes certain cereals, fruits, vegetables and legumes, see figure 1.

As a consequence gas may be produced and water-flux to the bowel is increased. This is a physiological process [11]. In patients v Figure 1. Examples of foods rich in FODMAP. Photo: [name] hypersensitivity leading to patient discc

Figure 2. FODMAPs are poorly absorbed in the small intestine and can cause gas production and abdominal symptoms (with permission from [1])

as illustrated in Figure 2

Thus, FODMAP restriction has been proposed as a treatment for IBS and has been documented to be efficient in the majority of patients [14-17] In a recent study from Sweden, the effect of FODMAP reduction in IBS patients was seen, but not superior to alternative, standard treatment [18]. In clinical practice, FODMAP restriction is performed under the guidance of a clinical dietician. The first step is usually to record the patient's diet, exclude all food items with high FODMAP content from diet, followed by a structured re-introduction again under close guidance of a clinical dietician. FODMAP restriction done by patients themselves after written or online guidance lacks scientific support. FODMAP restriction has been included in the most recent NICE guidelines (NICE guideline CG61Irritable bowel syndrome in adults www.nice.org.uk).

A low FODMAP diet may also have impact on faecal microbiota. A recent study in IBS patients indicates that the responsiveness to a low FODMAP diet may be predicted by the microbiota profiles[19].

Although FODMAP reduction may play a role in patients with diet treated coeliac disease, there are no published studies addressing this topic. In fact, there is a huge knowledge gap and unmet clinical need for studying FODMAP in other patient populations than those suffering from IBS.

3. Hypotheses, aims and objectives

The overall aim is to improve dietary treatment of coeliac patients with persistent gastrointestinal symptoms in spite of a strict gluten free diet.

The project has two main objectives:

- A) To investigate the prevalence of persistent gastrointestinal symptoms and assess the amount of FODMAP in the diet of coeliacs on a strict gluten free diet. This will be done with a web-based quest back tool in collaboration with the Norwegian Coeliac Association.
- **B)** To perform a randomized, controlled trial in coeliac disease patients with gastrointestinal symptoms, comparing a low FODMAP glutenfree approach to an ordinary gluten free diet. This part of the project will also validate questionnaires and biomarkers for the assessment of gluten-free diet adherence.

In addition, the present project will provide unique biological materials for biobank and ongoing projects in our coeliac group. This is basic and translational research and is beyond the scope of this application.

The target audience is adult, Norwegian patients who have been diagnosed with coeliac disease, but despite strict gluten free diet experience considerable gastrointestinal symptoms.

The project is aimed directly at patients being treated in our public health system. The project is closely related to activities at OUH Rikshospitalet and the University of Oslo (Centre for Immune Regulation and KG Jebsen Centre for Coeliac Disease Research). It is appropriate to cooperate with other hospitals in the South-East Region for patient recruitment. Norwegian Coeliac Disease Association (NCF) will also be an important partner through their newsletter, website and Facebook group. We have recruited patients in other studies in this way so that we know this is a good approach [20-25].

4. Project methodology

4.1. Project design, method selection and analyses

Study A: Prevalence of persistent GI-symptoms in coeliac disease

Setting

We have a rather unique situation in Norway as the majority of patients with coeliac disease are or have been members of the NCF, and communication electronically and on social media like Facebook is widespread. This will give us the opportunity to perform an online survey as, in fact, has been done in Canada [26]. However, in the mentioned study they did not record on going symptoms. Persistent symptoms has more recently been evaluated in a Finnish study using direct patient contact and written formulas [10]. We propose to use a web-based technology to interact with as many coeliac disease patients as possible.

Design

A national cross-sectional study exploring prevalence of persistent symptoms in treated coeliac patients.

Patients

Members of NCF will receive e-mail invitation to participate in the online survey, as well open invitations in relevant social media that target the coeliac disease population. This method gives the opportunity to include a large sample, and since we aim to obtain the number of participants needed for study B, the number of participants in this part of the project will be unlimited within the following inclusion criteria:

- Biopsy verified coeliac disease patient, 18-75 years of age
- Strict gluten free diet for at least 12 months

NCF has approximately 10 000 members. We expect a 30 % response rate, and aim to include 3000 patients in this study.

Methods

We will use web-based questionnaires to survey gastrointestinal symptoms, health related quality of life and diet adherence by questionnaire.

For recording of gastrointestinal symptoms we will use a published and validated questionnaire that was originally developed for IBS purposes, the Gastrointestinal Symptom Rating Scale, IBS version (GSRS-IBS) [27]. We, and others, have found that this form is very well suited to evaluate the burden of disease and symptom level for IBS-like symptoms in treated coeliac disease, and it is suitable for measuring the effect of interventions [28]. The questionnaire is translated to Norwegian. FODMAP intake will be estimated by use of a questionnaire developed by [name] & co-workers [29].

In the current project we will employ recently developed disease specific quality of life forms. First, the Coeliac Disease Questionnaire (CDQ), a disease specific health related quality of life measure for adults with coeliac disease [30]. The form is translated into Norwegian, but has not been tested. Second, the Coeliac Symptom Index (CSI) was published by our collaborator in US, professor [name] at Harvard University, Boston [31]. This questionnaire is already translated and approved by the Harvard group. The project will include testing and validation of these disease specific tools for coeliac disease. Other relevant questions may add to the survey by NCF.

This study will also enable us to compare the collected information between CD patients with and without persistent GI-symptoms. Those patients who score high on the reported outcomes, will, as part of the survey, be invited to participate in study B.

Study B. A randomized controlled trial in patients with persistent GI-symptoms

Design

We will follow recommendations for design of clinical trials evaluating dietary interventions in patients with persistent functional gastrointestinal disorders [32]. A cross-over design has been carefully considered but is not possible as patients cannot be de-educated. A flow-chart of the study is given in Figure 3.

Patients

CD patients selected from study A, and willing to continue to study B

Inclusion criteria

- Coeliac patients (18-75 years) treated with GFD for at least 12 months
- Normal CD serology and duodenal biopsy (Marsh 0-1)
- Persistent gastrointestinal symptoms defined by GSRS-IBS score of 30 or more
- Strictly adherent to GFD
- Living less than 2 hours from study centre

Intervention

• Both groups will follow strict gluten free diet (GFD). The intervention group will in addition receive instructions on how to follow a FODMAP diet (LFD).

Endpoint

- Primary endpoint will be change in gastrointestinal symptoms measured by GSRS-IBS score.
- Secondary endpoints will be changes in biomarkers like serology and faecal microbiota

01.06.2018

Adherence

Adherence to the diets will be monitored halfway in both groups. Assessment of dietary FODMAP and gluten intake will be obtained by 24-hour recall, which is a validated method for nutritional assessment in nutrition research [32]. Nutritional calculations will be done by the software Dietist Pro, which is implemented and used by dieticians at Oslo University Hospital, as well as in the other Nordic countries (www.kostdata.se/nb/dietist-net/dietist-net-pro).

Differentiated FODMAP calculations will be done by the software FoodWorks by our collaborators at the Monash University, Melbourne. To date, they are the only site that has a reliable FODMAP database based on food analysis.

Dietary assessment will also include evaluation of dietary adherence to the gluten-free diet by standardized dietician interview and by the coeliac disease adherence test (CDAT) [34]. There are few objective measures for diet adherence and the Norwegian translated CDAT version is not tested or implemented in Norwegian practice.

We will validate the CDAT questionnaire and recently suggested blood based tests for mucosal damage, the S-Intestinal Fatty Acid Binding Protein (S-IFABP) [35] and the faecal 33-mer peptide as a measure for gluten contamination [36]. Both these novel tests will be implemented at our clinical unit during 2018.

Figure 3 Flow-chart of study B. LFD: Low FODMAP diet. GFD: Gluten free diet

All partisipants will be offered follow-up visits for re-introduction of FODMAPS (intervention group) or instructions for LFD (control group).

Power calculation:

The primary endpoint for measuring effect of the low FODMAP diet will be GSRS-IBS total symptom score. From previous studies with coeliac disease patients and non-coeliac gluten sensitivity persons we know that a clinical significant difference in symptom score is present when group means are 22,5 (SD 8) and 29,5 (SD 11), respectively (based on our unpublished results from on going clinical trial). With a power of 80 % and a significance level of 0,05 we will need 31 patients in each group. To account for 15 % drop out, we aim to include 72 individuals.

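### Study A is presented as a national prevalence study, but its expected 30% response, open social-media route and link to Study B put the prevalence at risk of selection bias, plausibly upwards and of unknown size

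*Protocol*

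**What the plan says.** Section 3 makes the prevalence of persistent gastrointestinal symptoms part of the first of two main objectives, together with FODMAP intake. Section 4.4 lists the same two topics as the first planned paper. Section 4.1 (Study A, Design) describes the study as "A national cross-sectional study exploring prevalence of persistent symptoms in treated coeliac patients".

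Two recruitment routes are given under Study A, Patients. Association members are e-mailed, and there are "as well open invitations in relevant social media that target the coeliac disease population". On numbers the protocol says "NCF has approximately 10 000 members", followed by "We expect a 30 % response rate, and aim to include 3000 patients in this study". The number of participants is otherwise left unlimited, and the reason given is "since we aim to obtain the number of participants needed for study B".

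The link to the trial is explicit. At the end of Study A, Methods: "Those patients who score high on the reported outcomes, will, as part of the survey, be invited to participate in study B". Study B takes "CD patients selected from study A, and willing to continue to study B", and its inclusion criteria require a GSRS-IBS score of at least 30.

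The published figures that the protocol sets as background are in section 2.1: 10-20% (US) and 23% (Finland), with the investigators' expectation that Norwegian numbers are at least that high.

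**The concern.** A prevalence survey needs response to be unrelated to the condition being counted, or some means of seeing whether it is. Here 70% of e-mailed members are expected not to answer, the questionnaire is about symptoms, and the same survey is the way into a treatment trial for people with symptoms. A member who still has complaints has a reason to answer that a well member lacks. The open links add respondents who chose themselves from a group of unknown size, so no response rate can be calculated for the combined sample.

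The text available for this review has no neutral-invitation requirement, no reminder, no comparison of early and late responders, no separate reporting of the two routes, and no limit on how the result may be generalised.

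What is at stake is the prevalence part of a main objective and of the first paper. Any upward bias would run in the direction the investigators already expect. It could also be mistaken for a difference between countries, since section 4.1 says the Finnish study used direct patient contact and written forms.

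**Working it through.** **Inputs from the protocol.** About 10 000 members, 30% expected response and a target of 3000 (section 4.1); reference prevalences of 10-20% and 23% (section 2.1).

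**Input not in the protocol, assumed.** The response ratio k, meaning the probability of answering for a patient with symptoms divided by that for a well patient. Values 1.0, 1.25, 1.5 and 2 are used for illustration.

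**Step 1, the protocol's own figure.** 10 000 × 0.30 = 3000, which reproduces the target. It treats every member as eligible and counts nobody from the open links.

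**Step 2, sampling error.** With true prevalence p = 0.23 and n = 3000, treated as a simple random sample:

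half-width = 1.96 × √(0.23 × 0.77 / 3000) = 1.96 × 0.00768 = 0.0151, or about 1.5 points.

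**Step 3, observed prevalence under unequal response.** Observed = p·k / (p·k + 1 − p). The overall response is held at 30%, so well patients answer at 0.30 / (p·k + 1 − p) and patients with symptoms at k times that.

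| k | Response, symptoms / well | Observed if true value is 23% | Bias (points) |
|---|---|---|---|
| 1.0 | 30.0% / 30.0% | 23.0% | 0 |
| 1.25 | 35.5% / 28.4% | 0.2875 / 1.0575 = 27.2% | 4.2 |
| 1.5 | 40.4% / 26.9% | 0.345 / 1.115 = 30.9% | 7.9 |
| 2 | 48.8% / 24.4% | 0.46 / 1.23 = 37.4% | 14.4 |

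From a true 10%, the lower US figure, the observed values are 10.0%, 12.2%, 14.3% and 18.2%, with a half-width of 1.1 points. From a true 20% they are 20.0%, 23.8%, 27.3% and 33.3%, with a half-width of 1.4 points.

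**Step 4, how much imbalance the interval can absorb.** The formula in step 3 multiplies the true odds by k. The true odds are 0.23 / 0.77 = 0.2987.

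- Upper limit: (0.2451 / 0.7549) / 0.2987 = 1.09.
- Lower limit: (0.2149 / 0.7851) / 0.2987 = 0.92.

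The bias stays inside the half-width only for k between about 0.92 and 1.09. The upper end corresponds to roughly 32.0% of patients with symptoms answering against 29.4% of well patients.

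**Step 5, effect of sample size.** The sample size n does not appear in step 3. Recruiting more respondents narrows the interval in step 2 and leaves the bias unchanged.

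**The case against.** **Direction and size.** The protocol gives no response ratio. At k = 1 there is no bias, and below 1 it would be downwards. This stands. A reader might infer that the prevalence will be biased upwards, but the protocol supports only a risk, with the upward direction a reasonable inference from the design.

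**The trial offer comes after a high score.** Section 4.1 describes the Study B invitation as part of the survey and dependent on the scores given. The e-mail goes to members generally, and the social-media invitations are aimed at coeliac patients rather than at those with complaints. The invitation text is not shown, so it cannot be called slanted. This also stands, and it weakens the mechanism. It does not remove it: the protocol does not say that the invitation omits the trial, section 4.4 places advertising for participants in the same year as the survey, and the subject of the survey may itself attract people with symptoms. The statement in section 3 that "Norwegian Coeliac Disease Association (NCF) will also be an important partner through their newsletter, website and Facebook group" concerns recruitment for the project as a whole, so it is only background here.

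**Worst-case bounds.** A reader might combine 30% response with an observed 23% and conclude that the true value lies anywhere from 6.9% (0.30 × 0.23) to 76.9% (0.069 + 0.70). The documents do not support that calculation. It takes all 10 000 members as eligible, although the survey is restricted to biopsy-verified patients aged 18-75 on a strict diet for at least 12 months, and it takes all 3000 respondents as e-mailed.

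**This belongs in an analysis plan.** Weighting and the wording of results could be left there. Invitation text, reminders, a record of the route of entry and the association's membership totals are matters of conduct and are hard or impossible to recover after the survey closes.

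**Modest consequence.** The design is described as exploratory, objective A also covers FODMAP intake, and no formal comparison with other countries is planned. That limits the severity. Part of section 4 was also not available, so a safeguard stated there cannot be excluded.

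**Conclusion.** The point holds as a risk. A result described as national would rest on an expected 30% response, a second route with no denominator, and a survey that also recruits patients with symptoms. Under the assumed ratios of 1.25 to 2, a true 23% would be overstated by 4.2 to 14.4 points, several times the 1.5-point half-width. The actual ratio is unknown and could be 1. The firm part of the finding is how little imbalance is needed: outside about 0.92 to 1.09, the bias exceeds the half-width at 3000 respondents.

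This rests on a true prevalence near the Finnish figure, 3000 respondents treated as a simple random sample, and response that differs only by symptom status. It concerns Study A's prevalence. A reader might extend it to the trial, but Study B compares randomised groups among patients who have already been selected, so that comparison is unaffected. It is a cheap improvement that should be made before the survey runs.

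**What to change.** 1. In section 4.1 (Study A, Patients), specify an invitation addressed to all adult members, with or without complaints, that does not mention Study B. Keep the order already described under Methods, and state that the offer appears only after the GSRS-IBS has been submitted.
2. Send one reminder to e-mailed members, and compare prevalence between first-wave and reminder responders. This is an indirect check on symptom-related response.
3. Record the route of entry and report e-mail and open-link respondents separately. For e-mailed members, give the prevalence weighted to the association's aggregate age, sex and region beside the crude value. State that this is only a partial correction, because weighting cannot remove symptom-related response within those strata.
4. State the result as prevalence among responding patients, not as the national figure, and do not read a difference from 10-20% or 23% as a difference between countries.

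The cost is some extra work: invitation text, one reminder, a field for route of entry, one aggregate table from the association and a weighted analysis. Response may be slightly lower, and the weighted interval slightly wider.

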4.4 Plan for activities, visibility and dissemination

The time until the start of the project 01.06.2018 will be used for the completion of protocols and obtaining the necessary ethical approvals. The project is closely related to several of the projects we already have running in our group. Subproject with gluten provocation of treated coeliacs part of a South-East supported PhD project where PhD candidate will examine immune biological mechanisms of mucosal reaction to gluten. Since protocols are adjacent to each other, it is expected that all necessary approvals will be in place early. The following plan is submitted:

2018

- Completion of clinical report forms (CRF) for the two sub-studies
- Online Survey
- Planning and designing of the studies, application for REK, pilot testing, advertising for study participants
- · Recruitment and clinical assessment of treated coeliacs with persistent symptoms
- Researcher training in the PhD education program

2019

- Recruitment, study conduct
- Analysis and writing subproject A
- Treatment and follow-up of patients in subproject B (expected to take the entire year)
- Researcher training in the doctoral program

2020

- Completion of subproject B
- Analysis of results and paper writing
- Writing frame report to the PhD degree, disputation

Suggested titles of the papers:

- 1. Prevalence of persistent gastrointestinal symptoms and FODMAP intake in patients with coeliac disease
- **2.** Effect of FODMAP reduction in coeliac disease patients with gastrointestinal symptoms, a randomized, controlled trial
- **3.** Validation of questionnaires and biomarkers for the assessment of gluten-free diet adherence

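### Study A compares patients with and without symptoms on current FODMAP intake without recording whether they have already cut FODMAPs, so the contrast may be masked or reversed

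*Protocol*

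**What the plan says.** Protocol section 4.1 describes Study A as "A national cross-sectional study exploring prevalence of persistent symptoms in treated coeliac patients". Symptoms are scored with GSRS-IBS in a web survey. In the same methods text, "FODMAP intake will be estimated by use of a questionnaire developed by" a named group. After the list of instruments the protocol adds: "This study will also enable us to compare the collected information between CD patients with and without persistent GI-symptoms".

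That sentence does not name FODMAP intake, but intake is among the data collected. Objective A in section 3 is, besides prevalence, to "assess the amount of FODMAP in the diet of coeliacs on a strict gluten free diet". The first suggested paper in section 4.4 is titled "Prevalence of persistent gastrointestinal symptoms and FODMAP intake in patients with coeliac disease".

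Eligibility for Study A is biopsy-verified disease, age 18 to 75 and at least 12 months on a strict gluten-free diet. Neither the criteria nor the listed instruments refer to current or past FODMAP restriction. On such restriction, section 2.1 (The FODMAP concept) says: "FODMAP restriction done by patients themselves after written or online guidance lacks scientific support". It gives no frequency and does not link the remark to coeliac respondents.

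**The concern.** Exposure and outcome are measured at the same moment, and symptoms may themselves change the exposure. A patient who has cut FODMAPs and still has symptoms lowers mean intake in the symptomatic group. One who has cut them and improved is counted as symptom-free and lowers the mean there. The observed difference then mixes habitual intake with adaptation, and its direction cannot be judged without knowing who has adapted.

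The protocol makes such adaptation plausible. Section 2.1 likens persistent symptoms to irritable bowel syndrome, describes dietician-led FODMAP restriction as practice for that condition, and mentions restriction by patients themselves. Study A recruits through the patient association and social media. Section 4.1 rejects a cross-over for Study B because dietary teaching cannot be undone.

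At stake is how one comparison in the first paper is read. Similar or lower FODMAP intake in symptomatic patients could be taken as evidence that FODMAPs do not matter, when it may partly reflect patients who have already changed their diet. A later analysis plan cannot repair this, because the missing piece is a question in a one-time survey.

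**Working it through.** **The plan's own figure.** Section 4.1 gives about 10 000 members and a 30% response: 10 000 × 0.30 = 3000, as stated. The point does not contest this figure.

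**Bias in ratio form.** The documents give no input for this, so all values are assumptions. Let habitual intake be 10% higher in symptomatic patients, let restrictors halve their intake, and let x and y be the shares restricting among symptomatic and symptom-free patients as classified at the survey. Restrictors are taken to have the same habitual intake as the rest of their group.

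Observed ratio = 1.10 × (1 − 0.5x) / (1 − 0.5y)

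| x | y | Observed ratio |
|---|---|---|
| 10% | 0% | 1.10 × 0.95 = 1.045 |
| 20% | 0% | 1.10 × 0.90 = 0.99 |
| 40% | 0% | 1.10 × 0.80 = 0.88 |
| 20% | 10% | 0.99 / 0.95 = 1.04 |
| 40% | 30% | 0.88 / 0.85 = 1.04 |
| 20% | 20% | 0.99 / 0.90 = 1.10 |

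Setting the ratio to 1 gives x = 2 × [1 − (1 − 0.5y)/1.10].

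- y = 0: x = 2 × (1 − 0.909) = 18%.
- y = 10%: x = 2 × (1 − 0.864) = 27%.
- x = y: the ratio stays at 1.10, so there is no bias.

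**The same in SD units, with y = 0.** Observed difference = d − q × c, where d is the habitual excess, q the share of symptomatic patients who cut and c the size of the cut.

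- d = 0.2: zero at q = 20% with c = 1, or q = 40% with c = 0.5. With c = 1 and q = 30% it is 0.2 − 0.3 = −0.10 SD.
- d = 0.1: zero at q = 10% (c = 1) or 20% (c = 0.5).
- d = 0.3: zero at q = 30% (c = 1) or 60% (c = 0.5).

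**Does sample size protect?** Section 2.1 cites 23% with persistent symptoms in a Finnish study. Of 3000, that is 690 against 2310. The standard error is √(1/690 + 1/2310) = 0.043 SD, and the difference detectable with 80% power at two-sided 0.05 is 0.043 × (1.96 + 0.84) = 0.12 SD. At the 10% and 20% from US data it is 0.17 and 0.13 SD. Random error is small, so a biased difference could look precise.

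Whether it would be significant depends on the shares. With an assumed coefficient of variation of 0.4 to 0.8, a ratio of 0.88 is a difference of 0.12/0.8 = 0.15 to 0.12/0.4 = 0.30 SD, or about 3.5 to 6.9 standard errors. A ratio of 0.99 is at most 0.01/0.4 = 0.025 SD, which is less than one standard error.

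**The case against.** The strongest reply is that this is the ordinary limit of any cross-sectional survey, and that Study A claims nothing more. Objective A is descriptive. The sentence on comparison is general and also covers quality of life and diet adherence. The effect question belongs to objective B, which reads: "To perform a randomized, controlled trial in coeliac disease patients with gastrointestinal symptoms, comparing a low FODMAP glutenfree approach to an ordinary gluten free diet". That stands, and it confines the point to interpretation of one contrast. It does not remove it. Section 2.1 states the project's interest as "We specifically aim at investigating the impact of FODMAPon this frequent condition with" persistent symptoms, and a FODMAP contrast by symptom status reported in that setting invites a causal reading.

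A reader might infer that the protocol itself says symptoms drive patients to cut FODMAPs. It does not. It mentions self-directed restriction, and the guideline it cites concerns irritable bowel syndrome. The mechanism is plausible, but it is not documented in these respondents.

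A reader might also infer that Study B rests on this comparison. Nothing says so. Study A's stated role for Study B is recruitment, and section 4.4 puts the analysis of Study A in the same year as treatment in Study B.

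An item on restriction may exist out of sight. The questionnaire is not in the document, part of the protocol was not in the text reviewed, section 4.1 lets the patient association add questions, and section 4.4 has the forms still to be completed in 2018. This stands as a caveat. It is also why the change is cheap.

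Finally, never-restrictors are a selected group. Patients who improved by restricting are removed from the symptom-free side, and they may be the most FODMAP-responsive. This stands, and it limits the remedy.

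**Conclusion.** The point holds as a limit on Study A's comparison of FODMAP intake by symptom status. As described, that comparison cannot separate habitual intake from intake changed because of symptoms, so it could be masked or reversed. The prevalence estimate, the description of current intake, and Study B's endpoint, sample size and randomized comparison are untouched.

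The size is unknown because the restricting shares are unknown. The break-even values of about 18% (y = 0) and 27% (y = 10%) depend on the assumed 10% excess and halved intake. The figure of 18% should not be read as a general threshold, since it requires that no symptom-free patient restricts. What matters is how far restriction differs between the groups, and the survey as shown does not measure that. The documents do not support saying that a reversal will occur or that Study A is invalid. This is a low-cost improvement that cannot be made once the survey has closed.

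**What to change.** Add one survey item asking whether the respondent has changed diet to reduce FODMAPs: never, earlier or now; and if so, dietician-led or on their own.

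Report FODMAP intake by symptom status for all respondents, labelled as a description of current intake. Beside it, show the same comparison in those who never restricted, with restrictors as a separate group. The never-restrictor comparison should not replace the all-respondent one, because that group is itself selected.

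The cost is one more web question and smaller strata in the added display. If the survey has already closed without such an item, only the descriptive label and a stated limitation remain possible.
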